The Effect of Temporal Muscle Suspension on the Risk of Temporal Hollowing:
A Prospective Randomized Clinical Trial

[name]
Associate Professor
Department of Plastic and Reconstructive Surgery
Johns Hopkins School of Medicine

Johns Hopkins Hospital
[name]
[name]
[contact]
[contact]

Application No. : IRB00120812

The pterional approach to the cranio-facial region is an often-used approach by neurosurgeons. This surgical approach is used for access to intra-cranial abnormalities (ie. Tumors, trauma, or vascular insults). Temporal hollowing is a common complication that that can affect the patient both physically and emotionally. In an aesthetic region, it can represent a stigma of disease that prevents the patient from moving on with the normalcy of their disease-free lives. The hollowing generally occurs within 6 months from the index surgery. Currently the exact mechanism or incidence of this complication is not very well described.

The purpose of this prospective study is see if traditional techniques to the closure and temporal muscle suspension (TMS) after the pterional approach will show any differences in post-operative temporal hollowing (TH).

1. Objectives

The primary objective is to identify which patients undergoing a traditional pterional approach with 2 different surgical techniques for TMS will develop TH. Pre and post-operative CT scans will be reviewed and analysis with previously proven metrics will be performed.

2. Background

Surgical Details/Anatomy

The pterional approach is an indicated neurosurgical approach commonly used for anterior circular aneurysms, suprasellar lesions, and medial sphenoid wing tumors (1,2). A curvilinear incision from the midline widows peak and extending laterally to 1 cm anterior to the tragus of the ear, terminating within a skin crease, with preservation of the superficial temporal artery if possible. The temporalis fascia is encountered and divided. Either the entire temporalis muscle can be elevated or a cuff of temporalis muscle can be left on the cranium to facilitate closure and suspend the temporalis muscle. Subperiosteal dissection of the muscle is performed and the craniotomies are then accomplished. Reconstruction of the pterional approach can be accomplished with bony fixation of the bone flap. However, the TMS can be performed by:

Date: 10/24/2017
Principal Investigator: [name]
Application Number: IRB00120812

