1. Resuspension of the temporalis muscle to the cuff of muscle left on the temporal crest
or
2. Suturing the temporalis muscle directly to one of the bone plates that is used to for
fixation.

Current Literature

The TH can occur either due to direct injury to the muscle, atrophy from denervation or even loss of vascular supply (3). Modern neurosurgical techniques have led to great improvements of surgical and functional outcomes, however less attention has been paid to the post-operative complications of scarring and soft tissue deformities (4). There have been several techniques and alterations to the traditional pterional approach to overcome some of the surgical drawbacks such as TH. The most common published is the use of a minipterional (MPT) approach (5). However, the minimalist approach has been debated regarding its effectiveness due to the narrowing of the visual field and restricted maneuverability (6). In the Johns Hopkins experience a retrospective review performed by Huang et al. found the MPT a suitable alternative approach without suboptimal visualization and no instances of improper vascular clip applications (7). They also described limited temporal wasting in 96% of their patients. The obvious limitations to this study and much of the studies in the literature are that they are retrospective in design. Additionally, the primary objective of that study was to evaluate the safety and efficacy of a minimalist approach. To their credit the temporal hollowing was addressed with a placement of an artificial implant. To date there has not been a prospective study regarding the reconstructive placement of the bone flap and temporalis muscle after a pterional approach to the cranium. Elucidation of a surgical cause of TH may lead to a decrease in secondary surgeries and the inherit risks that are associated.

3. Study Procedures

This study will include all patients under the care of [name] MD who qualify for a pterional approach for management of their neurosurgical disease. A pre-operative CT scan will be performed using the Gordon/Stryker Maxillofacial protocol, which is performed as part of the patients routine workup. If

Date: 10/24/2017
Principal Investigator: [name]
Application Number: IRB00120812

the patient agrees to take part in the study, the patient will be randomized into 1 of 2 groups (randomization will take place by a coin flip).

Group Heads: Traditional pterional approach with a muscle cuff left for TMS

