Group Tails: Traditional pterional approach with TMS performed with a bone plate.

All patients will be assigned a confidential experimental number which will be linked to their MRN. The linking database identifying patients with their alphanumeric code will be stored on a single computer that is password protected. The password will only be given to the Co-Investigators on this IRB application.

Routine follow up will be performed at 1 week from surgery, 1 month, and lastly 6 months from surgery where a routine post-operative CT Scan will be performed.

Photographs will be taken on the lateral head for comparison. All identifying markers (eyes, nose, and lips, or skin lesions/tattoos) will be removed for privacy. All other care and services will be as per routine.

There will be no extra research procedures performed or asked of the patient.

Demographic data including age, gender, indication for surgery, length of surgical time, and complications will be recorded.

a. Study Duration

- a. The duration of the study will conclude 6 months after the last patient is enrolled. The study does not alter the normal amount of post-operative visits that are considered routine.

b. Blinding, including justification for blinding or not blinding the trial, if applicable.

There will be no blinding of the study as the operating surgeon will need to know which operation to perform.

c. Justification of why participants will not receive routine care or will have current therapy stopped.

- a. All patients enrolled will receive routine care

d. Justification for inclusion of a placebo or non-treatment group.

- a. There will be no role for a placebo group or a non-treatment group, as standard of care is some form of TMS

e. Definition of treatment failure or participant removal criteria.

- a. Participant removal will be initiated if they are unwilling to follow up in a routine fashion as outlined in the study protocol.

f. Description of what happens to participants receiving therapy when study ends or if a participant's participation in the study ends prematurely.

- a. All patients under the care of [name] will receive routine care and followup. This includes management of all surgical complications. There is no alteration of their routine care when the study ends or is prematurely ended.

4. Inclusion/Exclusion Criteria

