This study will include all patients over the age of 18 years who qualify for a pterional approach for their neurosurgical pathology. This will be determined by a clinical exam and plan by [name].

We will not include patients from protected populations, such as inmates or children. Patients will not be excluded on the basis of pregnancy.

5. Drugs/ Substances/ Devices

- a. The rationale for choosing the drug and dose or for choosing the device to be used. **N/A**
- b. Justification and safety information if FDA approved drugs will be administered for non-FDA approved indications or if doses or routes of administration or participant populations are changed. **N/A**
- c. Justification and safety information if non-FDA approved drugs without an IND will be administered. **N/A**

6. Study Statistics

- a. Primary outcome variable.
The primary end point and outcome variable will be the CT quantitative evaluation of TH. The pre and post operative CT scans will be analyzed by the same volume dimensional analysis which has been previously standardized by the lead authors' prior study on TH and cranioplasties (8). Percent change and volume analysis as compared to the non operated temporal region in a two dimensional and three dimensional view will be the primary outcome variable.
- b. Secondary outcome variables.
Secondary variables will include patient satisfaction for aesthetic results. Patients will be asked to rate their satisfaction of their aesthetic result on a scale from 1 to 10.

Date: 10/24/2017
Principal Investigator: [name]
Application Number: IRB00120812

- c. Statistical plan including sample size justification and interim data analysis.
A sample size of 30 patients was calculated (alpha error of .05 and a statistical power of 0.80) in order to detect a significant difference in post-operative TH in the 2 different surgical techniques. A paired Student t-test will be used to compare the degree of TH on the control side with the operated side. For the categorical data, a Fisher test and chi square test will be utilized. Differences less than 0.05 will be considered significant.
- d. Early stopping rules.
The study will be stopped early if patients with a certain type of TMS have favorable results.

7. Risks

- a. Medical risks, listing all procedures, their major and minor risks and expected frequency.
 - 1. There are no added risks to this study
- b. Steps taken to minimize the risks. **N/A**

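### Section 3b waives all blinding for a reason that covers only the surgeon, so the primary CT outcome may be measured by someone who knows the arm

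*Combined protocol and SAP*

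**What the plan says.** Section 3b (Blinding) states: "There will be no blinding of the study as the operating surgeon will need to know which operation to perform". It gives no other reason and mentions neither the person who measures the scans nor the patient.

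Section 6a defines the primary outcome: "The primary end point and outcome variable will be the CT quantitative evaluation of TH". The scans "will be analyzed by the same volume dimensional analysis which has been previously standardized" in the lead authors' earlier work, and the measure is "Percent change and volume analysis as compared to the non operated temporal region in a two dimensional and three dimensional view". Section 1 adds: "Pre and post-operative CT scans will be reviewed and analysis with previously proven metrics will be performed". None of these sentences names a reader, gives the number of readers or mentions masking. Section 3 sets the outcome visit at "6 months from surgery where a routine post-operative CT Scan will be performed".

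Two provisions in section 3 come closest to masking. Each patient receives a study number linked to the MRN, and the co-investigators hold the password to the linking database. Identifying features are removed from photographs, with privacy as the stated purpose. Section 6b adds a secondary outcome that patients rate themselves, satisfaction on a 1 to 10 scale.

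**The concern.** The surgeon must know the technique in the operating room. The primary outcome is measured on a scan taken 6 months later, and measuring a temporal region does not require knowing how the muscle was suspended. The stated reason therefore does not reach the step that produces the primary data.

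If the reader knows the arm and reads one arm even slightly differently from the other, the shift enters the comparison as though it were an effect of technique. Comparison with the non-operated side does not by itself remove it, because the shift could arise on the operated side. Section 6c sets the aim as to "detect a significant difference in post-operative TH in the 2 different surgical techniques", so a between-arm shift falls directly on the question being asked. Section 6d allows early stopping if one technique gives favorable results, so by-arm results may circulate while scans are still to be read.

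**Working it through.** **Step 1. Scope of the waiver against scope of its reason.**

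| Person | Blinding waived by 3b? | Reason given? |
|---|---|---|
| Operating surgeon | Yes | Yes: must know the operation |
| CT reader (primary outcome) | Yes, by the blanket wording | None |
| Patient (self-rated satisfaction) | Yes, by the blanket wording | None |

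**Step 2. Does another section mask the reader?** Sections 1 and 6a describe the CT analysis without naming who does it. The study number and the photograph editing in section 3 serve confidentiality, and neither is said to hide the arm. The linking file is open to the co-investigators. The gap stays open.

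**Step 3. The plan's own figure.** Section 6c gives 30 patients, alpha 0.05 and power 0.80, but no effect size or SD, so the figure cannot be reproduced. Solved backwards with 15 per arm and a two-sided test, the detectable difference is (1.960 + 0.842) × √(2/15) = 1.02 SD (normal approximation), or 1.06 SD with the t distribution. Masking the reader changes none of this.

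**Step 4. Illustration of an arm-dependent shift.** All of the following are assumptions:
- no true difference between techniques;
- 15 patients per arm (a coin flip does not guarantee this);
- two-sided 0.05 (section 6c does not state sidedness);
- a two-sample t-test, chosen because the stated aim is a between-technique difference. Section 6c itself names a paired test of control side against operated side, and these figures do not describe that test;
- the size b of the reading shift, in SD units.

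Formula: df = 15 + 15 − 2 = 28; critical value 2.048; noncentrality = b × √(15 × 15/30) = b × 2.739. The false-positive rate is the probability that a noncentral t variable falls outside ±2.048.

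| Assumed shift b (SD) | Noncentrality | False-positive rate |
|---|---|---|
| 0 | 0 | 5.0% |
| 0.05 | 0.137 | 5.2% |
| 0.1 | 0.274 | 5.8% |
| 0.2 | 0.548 | 8.3% |
| 0.3 | 0.822 | 12.5% |
| 0.5 | 1.369 | 26.2% |

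Simulation with 200,000 trials per shift gave 5.0, 5.2, 5.7, 8.3, 12.3 and 26.3%.

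A 20:10 split, with √(20 × 10/30) = 2.582 in place of 2.739, gives 5.7% at 0.1 SD and 23.9% at 0.5 SD, so the pattern does not depend on exact balance. Shifts of 0.1 SD or less leave the rate close to 5%.

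**The case against.** The strongest reply is that the outcome is a quantitative volume and percent-change measure, made by a method described as already standardized and referred to the patient's own other side. That leaves less room for reader discretion than a subjective rating would. How much operator judgment remains depends on a cited source outside these documents, and the gap could prove trivial. This stands as a limit on the likely harm. It does not close the gap: the documents do not say that the measurement is automated, and they do not argue that knowing the arm is harmless. Equally, they say nothing about reader variability, so they do not support calling any shift small.

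A second reply is that the scan may reveal the technique anyway. One arm involves "Resuspension of the temporalis muscle to the cuff of muscle left on the temporal crest"; in the other the muscle is sutured to a fixation plate. Since plates are described as holding the bone flap, a plate alone need not identify the arm. Whether a cuff or the attachment can be seen at 6 months is not settled. Masking could be partial, and the protocol should say so.

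A third reply is that the percentages rest on assumed shifts and on a test the plan does not name. That is correct, and they carry no weight as a forecast.

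**Conclusion.** The gap holds on the text: a study-wide waiver, a reason limited to the surgeon, and no masking of whoever measures the primary outcome. It is a weakness that should be corrected, mainly because correction costs so little.

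A reader might infer that the surgeon will measure the scans, or that the trial's result will be biased. The documents support neither: they do not identify the reader, and they show no shift, size or direction. A reader might also take the range of 5.2% to 26.2% as the expected false-positive rate. It is only what shifts of 0.05 to 0.5 SD would do under the assumptions listed. Confidence is high that the gap exists; nothing here measures its effect.

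**What to change.** Replace the statement in section 3b with wording such as:

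> The operating surgeon is unblinded. An existing study team member who did not take part in the surgery measures the pre- and post-operative CT scans under the study number, without access to the allocation, the MRN-code link or any by-arm results until all patients' measurements are locked. If an interim look is made, scans read for it are locked first and its by-arm results are withheld from the reader.

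The lock must cover all patients. The link is a single database and by-arm results span many patients, so release patient by patient could expose the arms of scans not yet read.

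Three further edits are needed:
- In section 3, provide that this reader does not hold the linking-database password, which now goes to the co-investigators.
- In section 3b, state whether patients are told their arm. Satisfaction is self-rated, and removing the blanket sentence would otherwise leave patient masking undefined.
- State that reader masking may be incomplete if the technique is visible on CT.

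The cost is protocol wording, some file handling to supply scans under the study number, and an access restriction. No added scan, visit or patient is needed. The documents do not show team roles, so the sponsor must confirm that an existing non-operating team member can read the scans. The benefit may be partial if the technique shows on the scan.

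### Section 6.a does not define what percent change is measured from, and the only CT test in 6.c has no pre-operative term, so asymmetry present before surgery may enter the hollowing measure.

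*Combined protocol and SAP*

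**What the plan says.** Section 1 sets the aim: "The primary objective is to identify which patients undergoing a traditional pterional approach with 2 different surgical techniques for TMS will develop TH". It adds: "Pre and post-operative CT scans will be reviewed and analysis with previously proven metrics will be performed".

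Section 3 supplies the baseline: "A pre-operative CT scan will be performed using the Gordon/Stryker Maxillofacial protocol, which is performed as part of the patients routine workup". It also schedules a routine CT at 6 months.

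Section 6.a states that "The pre and post operative CT scans will be analyzed by the same volume dimensional analysis", a method it attributes to an earlier cranioplasty study by the lead authors. The sentence defining the outcome follows and reads, up to its closing noun: "Percent change and volume analysis as compared to the non operated temporal region in a two dimensional and three dimensional view will be the primary". The reference named there is the other side. How the pre-operative values enter is not stated.

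Section 6.c names one test for the CT measure: "A paired Student t-test will be used to compare the degree of TH on the control side with the operated side". It mentions neither the pre-operative scan nor any adjustment for it. The same section says the sample size was set to detect a difference in hollowing between the two techniques.

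On who may enter, the introduction says: "This surgical approach is used for access to intra-cranial abnormalities (ie. Tumors, trauma, or vascular insults"). Section 4 lists no exclusion for temporal asymmetry that is already present.

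**The concern.** Developing hollowing is a change from the pre-operative state. A side-to-side contrast at 6 months equals that change only if the two sides matched before surgery. Natural asymmetry, or a tumour or trauma on the side to be operated on, would break the match, and the eligibility criteria admit such patients.

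Two analysts could therefore follow 6.a and compute different primary outcomes. One would take each side's percent change from before to after surgery and compare the sides, which uses the pre-operative CT. The other would take the percent difference between the sides at 6 months, which does not. The test in 6.c does not settle the matter.

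On the second reading, a patient with a smaller operated side before surgery is scored as hollowed, and a patient with a larger one is scored as protected. With about 15 patients per arm, the extra spread also weakens the comparison of techniques. The scan that would remove it is already taken.

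**Working it through.** **1. The plan's own figure.** The plan states: "A sample size of 30 patients was calculated (alpha error of .05 and a statistical power of 0.80"). It gives no effect size, SD or rate, so 30 cannot be reproduced, only back-solved. Two-sided t-tests at 80% power imply a standardised difference of 1.06 for 15 against 15, or 0.53 for a paired test on 30 pairs. The plan states neither.

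**2. Model.** For each patient let A be the side difference before surgery, H the new hollowing, and e1 and e2 the measurement errors of the two side differences.
- Pre-operative side difference: X = A + e1
- 6-month side difference: Y = A + H + e2
- Post-minus-pre change: Y − X = H + e2 − e1

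A remains in Y and cancels in Y − X.

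**3. The paired test of 6.c on 6-month values, with no new hollowing.** The input is the mean of A in units of the SD of the side difference. The documents give no value, so a range is assumed. With 30 pairs and two-sided 0.05 (noncentral t):

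| Mean prior asymmetry (SD units) | Probability of a significant result |
|---|---|
| 0 | 5% |
| 0.1 | 8% |
| 0.25 | 26% |
| 0.5 | 75% |

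The side comparison is biased only when mean asymmetry is not zero.

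**4. Comparing the techniques.** Assumptions not in the documents: 15 per arm, SD of H 10% of volume, SD of each measurement error 2%, and asymmetry SD a of 3, 5, 8 or 10%.
- SD of the change = √(10² + 2 × 2²) = 10.39. The effect giving the change score 80% power is 1.06 × 10.39 = 11.0 points.
- SD of Y unadjusted = √(10² + a² + 2²).
- Residual SD of Y after adjustment for X = √(10² + a² + 2² − a⁴/(a² + 2²)). The ANCOVA power uses 27 degrees of freedom and allows for chance imbalance in X.
- SD of the chance difference between arms in A = a√(2/15).

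| a | SD of Y | Power, Y unadjusted | Residual SD | Power, ANCOVA | Chance imbalance SD (points) |
|---|---|---|---|---|---|
| 3 | 10.63 | 78% | 10.33 | 79% | 1.1 |
| 5 | 11.36 | 73% | 10.37 | 79% | 1.8 |
| 8 | 12.96 | 61% | 10.38 | 79% | 2.9 |
| 10 | 14.28 | 53% | 10.38 | 79% | 3.7 |

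The ANCOVA figures lie between 78.5 and 78.9% before rounding.

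**5. When the baseline does not help.** With a = 0 and measurement SD 2%, power is 81.5% unadjusted, 80% for the change score and 79.9% for ANCOVA. With measurement SD 5%, a = 3% and the same effect, power is 71% unadjusted, 66% for the change score and 70% for ANCOVA. The change score falls below the unadjusted outcome whenever measurement SD exceeds asymmetry SD. ANCOVA loses at most about 2 points in these cases and gains up to about 25 (53% to 79% at a = 10 and measurement SD 2%).

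**The case against.** The strongest reply is that 6.a may already do what is needed. The sentence before the outcome sentence says both scans are analysed, and the outcome begins with a percent change. Read in order, that can mean the pre-to-post change on the operated side relative to the other side, which removes baseline asymmetry. The test in 6.c can be read the same way if the degree of hollowing on each side is itself a pre-to-post change. The cited measurement study may also define the quantity, though the documents do not reproduce its definition.

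This stands as far as it goes. A reader might infer that the plan ignores the pre-operative CT and counts prior asymmetry as hollowing. The documents do not support that; they leave the reading open. What remains is that the primary outcome has no single formula, and that 6.c neither supplies one nor mentions the baseline.

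A reader might also infer that asymmetry biases the comparison of techniques. It does not: the coin flip balances it in expectation, and the standard error already allows for chance imbalance. The cost there is precision.

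Finally, every SD in the illustration is assumed, and 6.c names no between-technique test of the CT measure to which the power figures could apply. That omission is a separate and larger gap. Filling it would still leave open which quantity is compared.

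**Conclusion.** The point holds as a gap in definition with a conditional consequence. Section 6.a does not say what the change is measured from or how the pre-operative CT enters, and 6.c omits the pre-operative CT.

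If 6-month values are used, the within-patient side test can declare hollowing where none developed, with probability 8 to 75% for an assumed mean asymmetry of 0.1 to 0.5 SD, against the nominal 5%. This vanishes if mean asymmetry is zero. The comparison of techniques stays unbiased, but power falls to between 78 and 53% under the assumptions in step 4, against about 79% with adjustment. If asymmetry is negligible there is nothing to gain. The documents contain no data on asymmetry, hollowing or measurement error, so these sizes are illustrations. The change is worth making because both scans are already planned.

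**What to change.** In 6.a, write one formula for the primary quantity: Y = 100 × (operated minus non-operated volume at 6 months) / (non-operated volume on the pre-operative CT).

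In 6.c, compare the two techniques on Y by ANCOVA, adjusting for X = 100 × (operated minus non-operated volume) / (non-operated volume), both taken from the pre-operative CT.

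For any statement that a patient developed hollowing, use Y − X, the post-minus-pre change in side difference. Before-to-after change on the operated side alone is not a substitute, because volume loss affecting both sides over 6 months would count as hollowing.

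If the sponsor already intends a pre-to-post change, 6.a should say so and give the formula, and 6.c should say that the paired test uses it.

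The cost is wording, one degree of freedom, and at most about 2 points of power if asymmetry is negligible. No scan or visit is added.

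### Section 6.c names no between-technique test for the CT outcome; when one is added, it should adjust for the pre-operative CT measure (minor, precision only)

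*Combined protocol and SAP*

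**What the plan says.** Section 3 (Study Procedures) obtains the baseline scan from every patient as part of routine workup: "A pre-operative CT scan will be performed using the Gordon/Stryker Maxillofacial protocol". It places the post-operative CT at 6 months. Section 6.a puts both scans on one scale: "The pre and post operative CT scans will be analyzed by the same volume dimensional analysis". The outcome is described in these words, without a formula: "Percent change and volume analysis as compared to the non operated temporal region in a two dimensional and three dimensional view will be the primary". Percent change could therefore be taken from the pre-operative value or from the opposite side.

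Section 6.c gives the sample size: "A sample size of 30 patients was calculated (alpha error of .05 and a statistical power of 0.80"). The purpose it states for that number is this: "in order to detect a significant difference in post-operative TH in the 2 different surgical techniques". The only test it names for a continuous measure is a paired Student t-test of the control side against the operated side. Fisher and chi-square tests are named for categorical data. Neither a test of one technique against the other on the CT measure nor a covariate appears anywhere in the document.

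**The concern.** The trial is sized for a contrast between randomised groups, but the named continuous test contrasts two sides of the same head. It can show that hollowing occurred. It cannot show that one technique produces less of it. A between-technique analysis therefore has to be written.

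The natural unadjusted choices are a two-sample comparison of the 6-month measure or of pre-to-post change. Each fixes the slope of post on pre in advance, at 0 for the 6-month value and at 1 for change. ANCOVA estimates that slope from the data. Apart from one degree of freedom, it is no less efficient than either. With about 15 patients per arm and a baseline already measured for each of them, a wider interval than necessary would be an avoidable cost.

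**Working it through.** **Inputs from section 6.c.** N = 30, taken as the total; "alpha error of .05"; "a statistical power of 0.80". Sidedness is not stated ("Differences less than 0.05 will be considered significant"), so two-sided is assumed. No effect size, SD or pre-post correlation (rho) is given.

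**The plan's own figure.** N = 30 cannot be reproduced without an effect size and SD. It can only be back-solved. For a two-sample t-test at 15 v 15 (28 df, two-sided 0.05), 0.80 power needs a standardised difference d = 1.06. Other readings imply other values: 0.93 if one-sided, 0.74 if 30 is per arm, and 0.53 if 30 was sized for the paired side-to-side test. Nothing in the documents selects among them. The 0.80 used below is therefore an assumed starting point and not a confirmed property of the trial.

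**Method.** Set the post-operative SD to 1 and the pre-operative SD to k. Then:
- variance of the 6-month value: 1
- variance of change: 1 + k² − 2·rho·k
- ANCOVA residual variance: 1 − rho²
- V = ANCOVA residual variance divided by the comparator's variance
- small-sample factor for estimating the slope: 1 + 1/26 = 1.038

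The unadjusted noncentrality is 1.060/√(2/15) = 2.90. For ANCOVA it is 2.90/√(1.038·V), on 27 df. Example at V = 0.75: 2.90/√0.779 = 3.29, which gives power 0.887.

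**Comparator: 6-month value (V = 1 − rho²; k does not matter)**

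| rho | V | ANCOVA power |
|---|---|---|
| 0 | 1.00 | 0.78 |
| 0.3 | 0.91 | 0.82 |
| 0.5 | 0.75 | 0.89 |
| 0.7 | 0.51 | 0.97 |

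**Comparator: change, equal SDs (k = 1, so V = (1 + rho)/2)**

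| rho | V | ANCOVA power |
|---|---|---|
| 0.3 | 0.65 | 0.93 |
| 0.5 | 0.75 | 0.89 |
| 0.7 | 0.85 | 0.85 |
| 0.9 | 0.95 | 0.80 |
| 0.95 | 0.975 | 0.79 |

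**Comparator: change, smaller pre-operative SD**

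| k | rho | V | true slope rho/k | ANCOVA power |
|---|---|---|---|---|
| 0.7 | 0.3 | 0.91/1.07 = 0.85 | 0.43 | 0.85 |
| 0.7 | 0.5 | 0.75/0.79 = 0.95 | 0.71 | 0.80 |
| 0.7 | 0.7 | 0.51/0.51 = 1.00 | 1.00 | 0.78 |
| 0.5 | 0.3 | 0.91/0.95 = 0.96 | 0.60 | 0.80 |
| 0.5 | 0.5 | 0.75/0.75 = 1.00 | 1.00 | 0.78 |
| 0.5 | 0.7 | 0.51/0.55 = 0.93 | 1.40 | 0.81 |

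Simulation (40,000 trials per setting, bivariate normal) agrees with every row to within about 0.003. A separate simulation of percent change from the pre-operative value (20,000 trials per setting, equal SDs, pre-operative coefficient of variation 20% assumed) gave 81.0%, 81.1% and 80.8% at rho 0.3, 0.5 and 0.7, against 92.5%, 89.0% and 85.0% for ANCOVA.

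The low point, about 0.78, occurs where the comparator already uses the right slope: rho = 0 for the 6-month value, rho/k = 1 for change.

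**The case against.** The strongest case against is that the gain may be nil. The proposed covariate is asymmetry before surgery; the outcome is asymmetry after surgery on one side. If hollowing varies between patients, the post-operative SD may well exceed the pre-operative SD. At rho 0.5 the gain over change is then about nil at k = 0.7, and about 2 points are lost at k = 0.5. An unadjusted analysis of change is also valid. All of this stands, and it is why the point is minor.

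Three stronger readings are tempting, and the documents support none of them.

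- A reader might infer that an unadjusted comparison of the techniques is planned and needs only a covariate. Section 6.c contains no such comparison, so adjustment belongs inside the missing test.
- A reader might take about 9 points as the expected gain, because both comparators give 0.89 at rho 0.5. That rests on equal SDs for the change comparator, on an assumed rho, and on a starting power of 0.80 that cannot be verified.
- A reader might treat chance baseline imbalance as a bias. At 15 v 15 the baseline mean difference has an SD of √(2/15) = 0.37 SD, so gaps will occur. Under randomisation, however, the unadjusted estimate is unbiased and its standard error already allows for them. This is the same precision point and not a second harm.

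**Conclusion.** The point holds as a minor improvement, to be made together with adding the between-technique test. That missing test is the larger defect. The documents establish that a baseline on the outcome's own scale is collected and that no analysis uses it as a covariate. They do not establish how much precision that forgoes.

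Across the assumptions tabulated, power moves from an assumed 0.80 to between about 0.78 and 0.97. The figures assume 15 v 15, two-sided 0.05, normal data and no dropout. The case for adjusting rests on the asymmetry: at most about 2 points lost, with possible gains several times larger, and no need to guess the slope in advance.

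**What to change.** In section 6.c, specify the between-technique analysis as a linear model (ANCOVA):
- outcome: the 6-month operated-versus-opposite-side CT measure
- factor: technique, as randomised
- covariate: the same measure from the pre-operative CT

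Report the adjusted difference between techniques with its 95% CI. Keep percent change as a descriptive summary. The paired side-to-side test can stay as a within-patient description, but it should not stand in for the comparison the trial is sized to make.

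The cost is one sentence and one extra model term. No new scans, readers or patients are needed. The price is one degree of freedom, at most about 2 power points if the unadjusted analysis would already have used close to the right slope.
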